DLT Evaluable	
 All subjects fulfilling the 'All Treated' population criteria, and having met the following adequate exposure criteria: 
 For Schedule 1 (once every 3 weeks dosing) subjects received a complete infusion in cycle 1. For Schedule 2 (once weekly dosing for 3 consecutive weeks, 1 week rest) subjects receive three infusions, two of which must be complete infusions, in cycle 1. (as increases up to $\leq 30\%$ are implemented between cohorts, less than 2 complete infusions would result in a total dose closer to the previous dose investigated). (Schedule 2 was not explored in the study) Any subject in the "All Treated" population who experiences a DLT, as defined in Section 3.3.3 of the protocol will also be included in the DLT evaluable population regardless of exposure. 	
 Summary of DLT, for Part 1 only

Population	Definition / Criteria	Analyses Evaluated
Pharmacodynamic	
 The 'Pharmacodynamic (PD) Population' is defined as those subjects in the "All Treated" population from whom at least one PD sample was obtained, analyzed, and was measurable. 	
 PD
Pharmacokinetic (PK)	
 All subjects in the 'All Treated' population who had at least 1 non-missing PK assessment (Non-quantifiable [NQ] values will be considered as non-missing values). 	
 PK

Refer to [Appendix 12](#): List of Data Displays which details the population used for each display.

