Serum (cytokines/chemokines)		X ¹⁹	X			X ¹⁹	At predose and EOI on D1 of each cycle	X	
Serum (anti-drug-antibodies)	X					X ²⁰	At the start of cycles 3 ²⁰ , 6 ²⁰ , 9 ²⁰ , 12 ²⁰ and 16 ²⁰	X	
Plasma-cfDNA	X							X	
Peripheral blood (flow for TBNK)	X ¹⁵					X ¹⁵	At the start of each cycle ¹⁵	X ¹⁵	
Serial Pharmacokinetics (blood)		X ²¹	X ²¹	X ²¹	X ²¹	X ²¹	C3D1 only ²¹	X ²²	
Urine PK	X ²³					X ²³	Day 1 of cycles 4 ²³ , 7 ²³ , 10 ²³ , 13 ²³ , 16 ²³		
Premedication if needed		X				X	At the start of each cycle		
GSK2857916 administration		X ²⁴				X ²⁴	X ²⁴		
Steroid eye drops		X ²⁵				X ²⁵	X ²⁵		
Adverse Events							Continuous		

Time and Events Table for Full Study (Cycle = 21 days)									
Study Assessments ¹	Screen ²	Day 1 C1	Day 2 C1	Day 8 C1	Day 15 C1	Day 1 C2	D1 of C3-C16	End of Study Treatment	3-Month Off-study Follow-up
Concomitant Medications	X	Continuous							
Survival Status									X ²⁶
Subsequent Treatment									X ²⁶

- Assessments scheduled on days of dosing should be done prior to drug administration, unless otherwise specified. All other assessments can be ± 3 days of scheduled occurrence unless otherwise specified.
- All Screening assessments must be performed within 14 days prior to first dose unless otherwise specified. Informed Consent must be signed before any study-specific assessments are performed.
- Screening examination to include BCVA (best-corrected visual acuity), slit lamp examination (with special focus on cornea), intraocular pressure, and dilated fundoscopic examination may be performed within 21 days prior to first dose.
- On-study exams to include BCVA (best-corrected visual acuity) and slit lamp examination (with special focus on cornea); window for exams is up to 3 days prior to dosing.
- On initial (first infusion) dosing day, vital signs must be assessed at pre-dose (within 30 minutes prior to SOI), +10 minutes and +30 minutes (±5 min) after SOI, EOI, and 1 hour post EOI. On subsequent dosing days, vital signs must be assessed at pre-dose (within 30 minutes prior to SOI), +30 minutes after SOI, and EOI. The Sentinel Subject must be observed for at least 24 hours post EOI. **On days where vital sign timepoints align with PK sampling timepoints, vital signs should be assessed prior to PK samples being drawn.**
- If completed within 72 hrs prior to the first dose, this assessment need not be repeated on Day 1 of Cycle 1. Refer to Table 15 of the protocol for comprehensive list of lab tests.

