16.7. Appendix 7: Reporting Standards for Missing Data

16.7.1. Premature Withdrawals

Element	Reporting Detail
General	
 • Subject study completion (i.e. as specified in the protocol) was defined as: 
 ○ For Part 1 (dose-escalation phase), a completed subject is one who has completed at least 1 cycle of study treatment and an End of Study Visit without events causing them to withdraw or discontinue from the study for reasons listed in Section 6.3 of the protocol. ○ For Part 2 (expansion cohort), a completed subject is one who has received at least one dose of study treatment without events causing them to withdraw or discontinue study treatment for reasons listed in Section 6.3 of the protocol and completed an End of Study Visit. ○ A participant will be considered to have completed the study if he or she has received at least one dose of the study treatment and, has died before the end of the study, has not been lost to follow-up, or has not withdrawn consent from study participation. • Withdrawn subjects may be replaced in the study. • All available data from participants who were withdrawn from the study will be listed and all available planned data will be included in summary tables and figures, unless otherwise specified.

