3.0101	All Treated	AE1	Summary of Adverse Events of Maximum Grade 3 or Higher by System Organ Class and Preferred Term (Part 2 MM)	Report for: Part 2 MM, (Summarize: only for 3.4 MM)	SAC [A]
3.0102	All Treated	AE1	Summary of Adverse Events of Maximum Grade 3 or Higher by System Organ Class and Preferred Term (All Treated MM)	Report for: All Treated MM, (Summarize: Total).	SAC [A]
3.0103	All Treated	AE1	Summary of Adverse Events of Maximum Grade 3 or Higher by System Organ Class and Preferred Term (Part 2 NHL)	Report for: Part 2 NHL, (Summarize: only for 3.4 NHL)	SAC
3.0170	DLT Evaluable	DL1	Summary of Dose-Limiting Toxicities during the Determinative Period (Part 1) (Day 1-21)	Report for: Part 1, (Summarize: by ascending dose level, Total). Section 3.3.3 of the protocol: An event will be	SAC [A]

CONFIDENTIAL

BMA117159

Safety: Tables					
No.	Population	IDSL / Example Shell	Title	Programming Notes	Deliverable [Priority]
				considered a DLT if its relationship to the investigational agent cannot be ruled out occurs within the DLT reporting period (first 21 days of treatment for schedule 1, and first 28 days for schedule 2)	
Serious and Other Significant Adverse Events					
3.0700	All Treated	AE16	Summary of Serious Adverse Events by System Organ Class and Preferred Term (Number of Participants and Occurrences) (Part 1)	Report for: Part 1, (Summarize by ascending dose level, Total). Include baseline values.	SAC [A]
3.0701	All Treated	AE16	Summary of Serious Adverse Events by System Organ Class and Preferred Term (Number of Participants and Occurrences) (Part 2 MM)	Report for: Part 2 MM, (Summarize: only for 3.4 MM). Include baseline values.	SAC [A]
3.0702	All Treated	AE16	Summary of Serious Adverse Events by System Organ Class and Preferred Term (Number of Participants and Occurrences) (All Treated MM)	Report for: All Treated MM, (Summarize for Total). Include baseline values.	SAC [A]
3.0703	All Treated	AE16	Summary of Serious Adverse Events by System Organ Class and Preferred Term (Number of Participants and Occurrences) (Part 2 NHL)	Report for: Part 2 NHL, (Summarize for Total). Include baseline values.	SAC
3.0080	All Treated	AE1	Summary of Drug-Related Serious Adverse Events by System Organ Class and Preferred Term (Part 1)	Report for: Part 1, (Summarize: by ascending dose level, Total).	SAC [A]

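### The Schedule 1 DLT Evaluable set requires one complete infusion but no observation over Days 1-21, so an early leaver without a DLT counts as a full non-DLT in the reported Part 1 DLT summary

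*SAP*

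**What the plan says.** Section 4 (Analysis Populations) sets an exposure test for DLT Evaluable. The Schedule 1 test is: "For Schedule 1 (once every 3 weeks dosing) subjects received a complete infusion in cycle 1". No minimum observation time is given. An All Treated subject who has a DLT "will also be included in the DLT evaluable population regardless of exposure". The only use assigned to the population is "Summary of DLT, for Part 1 only".

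Section 16.12.8 (Safety Tables) names DLT Evaluable as the population for Table 3.0170, titled "Summary of Dose-Limiting Toxicities during the Determinative Period (Part 1) (Day 1-21)". Its programming note gives the DLT reporting period as "first 21 days of treatment for schedule 1, and first 28 days for schedule 2". Section 16.12.13 uses the same population and the same 21 days for Listing 1.0220.

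Two other places bear on the point:

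- Section 16.7.1 defines study completion in Part 1: "a completed subject is one who has completed at least 1 cycle of study treatment", together with an End of Study Visit. It also allows withdrawn subjects to be replaced. Neither statement is tied to DLT evaluability.
- Section 16.2.2.1 schedules ocular exams at screening and then at Cycle 2 Day 1, where the "window for exams is up to 3 days prior to dosing".

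**The concern.** The population and the window do not match. A Schedule 1 subject qualifies on Day 1, when the infusion ends, but the table claims to describe 21 days. Someone who progresses, withdraws, dies of disease or changes therapy on, say, Day 5 without a DLT is counted as if the remaining 16 days had been watched and found clear. For subjects with a complete infusion, the missing observation rule can only lower the reported rate, because DLTs are always counted.

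Determining the MTD is among the study's primary objectives (Section 2.2), and Part 1 cohorts are small: a single-subject run-in, then three or more per cohort (Section 3.1.1.1). One misclassified subject therefore moves a cohort's rate a long way.

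**Working it through.** The SAP states no DLT rate, cohort result or early-exit count, so there is no planned figure to reproduce. All data below are assumed.

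**1. Crude rate.** Remove one early leaver without a DLT from the denominator.

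| Current definition | With a 21-day requirement |
|---|---|
| 1/3 = 33.3% | 1/2 = 50.0% |
| 1/6 = 16.7% | 1/5 = 20.0% |
| 2/6 = 33.3% | 2/5 = 40.0% |

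**2. Expected rate.** Let p be the true 21-day DLT rate, f the share of subjects leaving early, and g the share of their DLT risk already observed when they leave. If leaving is unrelated to DLT risk:

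- Current definition: p × [1 − f(1 − g)].
- Revised definition (ratio of expected counts): p × [1 − f(1 − g)] / [1 − f(1 − pg)].

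With p = 33%, the current definition gives:

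| f | g = 0 | g = 0.5 |
|---|---|---|
| 5% | 31.4% | 32.2% |
| 10% | 29.7% | 31.4% |
| 1/6 | 27.5% | 30.3% |
| 1/3 | 22.0% | 27.5% |

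The revised definition returns 33% when g = 0. It runs slightly high when g > 0: at f = 1/6 and g = 0.5 it gives 0.3025 / 0.8608 = 35.1%. The two definitions therefore sit on either side of the true rate.

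**3. Reassuring cohort results at p = 33%.**

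- No DLT in 3: 0.67³ = 0.301 if all are observed; 0.67² = 0.449 if one is not observed at all.
- At most 1 DLT in 6: 0.67⁶ + 6 × 0.33 × 0.67⁵ = 0.358; with only five observed, 0.67⁵ + 5 × 0.33 × 0.67⁴ = 0.468.

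**4. The opposite push.** Take three subjects: one DLT after a complete infusion, one complete infusion without a DLT, and one incomplete infusion without a DLT. The last is excluded, so the table shows 1/2, not 1/3. Had that subject had a DLT, he or she would have been included.

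**5. N-CRM, only if it used this population.** Inputs are the prior in Section 3.1.1.2 (means −1.3281 and −0.795; SDs 1.7153 and 1; correlation −0.9352; reference dose 0.72 mg/kg), a binomial likelihood, and the 0.25 over-dose limit in Section 3.1.1.1. The posterior was computed on a grid. The assumed history is 0/1 at each of 0.03 to 0.48 mg/kg and 0/3 at 0.96 mg/kg, with the 1.92 mg/kg cohort varied. P(DLT rate ≥ 33%) at 3.4 mg/kg:

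| Data at 1.92 mg/kg | Data at 3.4 mg/kg, leaver counted | Leaver excluded | Crosses 0.25? |
|---|---|---|---|
| 0/3 | 1/3: 0.268 | 1/2: 0.341 | No, both above |
| 0/4 | 1/3: 0.246 | 1/2: 0.315 | Yes |
| 0/6 | 1/3: 0.208 | 1/2: 0.270 | Yes |
| 0/4 | 1/6: 0.119 | 1/5: 0.152 | No, both below |

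Counting the leaver lowers the probability every time. Whether the limit is crossed depends on the history.

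**The case against.** A reader might infer that the DLT rate behind the MTD is diluted. The document does not support that:

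- Section 4 assigns the population to the DLT summary only. Section 3.1.1.1 says the N-CRM uses all toxicity information available and describes it as supportive to a primary 3+3 design. Section 3.1.1.3 rests the next dose on the totality of the data.
- Rules on evaluability and replacement for escalation may be in the protocol, which is not at hand.
- Escalation was over. This RAP took effect on 06-NOV-2018, and Section 5.1 already lists 3.40 mg/kg for both Part 2 cohorts. The table is retrospective and descriptive, and no further N-CRM run is planned.

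These points stand, and they limit the finding to the reported Part 1 summary. Two more also stand. Dilution needs actual early leavers, and none is documented. The incomplete-infusion rule works the other way.

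It is also true that Listing 1.0210 shows dose-limiting events for all treated myeloma subjects without a Day 1-21 limit in its title, and that the discontinuation, withdrawal and death listings would let a reader trace early leavers. That helps reconstruction but does not correct the denominator of Table 3.0170.

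Two further readings go too far. The one-cycle rule in Section 16.7.1 concerns study completion, so it is not an observation rule that Section 4 forgot to apply. The ocular exam timing is not a contradiction either: with a window of up to 3 days before a nominal Day 22 dose, the exam can fall on Days 19-21, and adverse events are recorded continuously. It is a separate timing question.

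**Conclusion.** The mismatch is real and lies within the SAP: evaluability is fixed by a Day 1 event, while the summary covers 21 days. Each early leaver without a DLT is counted as a full non-DLT. In cohorts of 3 to 6, one such subject shifts the reported rate by about 3 to 17 percentage points (20.0% to 16.7%; 50.0% to 33.3%). This holds only if such subjects exist. The net direction of the whole definition is not fixed, because of the incomplete-infusion rule.

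An effect on the MTD is possible but not shown. It would need the N-CRM to have used this population and a DLT history close to the 0.25 limit, and the SAP documents neither.

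**What to change.** 1. In Section 4, define Schedule 1 DLT Evaluable as a complete Cycle 1 infusion and observation through the 21-day DLT period, or a DLT within that period.
2. List the complete-infusion subjects excluded for incomplete observation, with day and reason of exit.
3. Show Table 3.0170 under both the current and the revised definition. The revised set still admits early leavers only when they have a DLT, so the pair is more informative than either alone.
4. State which population fed the N-CRM.
5. Separately, reconcile the timing of the first on-study ocular exam (Section 16.2.2.1) with the Day 1-21 window of Table 3.0170, so that it is clear how a finding first seen at that exam is reported.

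The cost is a wording change, one short listing and a second version of one table. The downside is that a few subjects may leave the DLT denominator.

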4.1. Protocol Deviations

Important protocol deviations (including deviations related to study inclusion/exclusion criteria, conduct of the trial, patient management or patient assessment) will be summarised and listed.

Protocol deviations will be tracked by the study team throughout the conduct of the study in accordance with the Protocol Deviation Management Plan [08May2017, Version 6.0].

- Data will be reviewed prior to freezing the database to ensure all important deviations are captured and categorised on the protocol deviations dataset.
- This dataset will be the basis for the summaries and listings of protocol deviations.

A separate summary and listing of all inclusion/exclusion criteria deviations will also be provided. This summary will be based on data as recorded on the inclusion/exclusion page of the eCRF.

5. CONSIDERATIONS FOR DATA ANALYSES AND DATA HANDLING CONVENTIONS

5.1. Study Treatment & Sub-group Display Descriptors

Treatment Group Descriptions				
RandAll NG		Data Displays for Reporting		
Code	Description ^[1]	Description ^[2]	Data Display	Order in TLF
A	Active Treatment	GSK2857916 0.03 mg/kg (Part 1 MM)	0.03 mg/kg	1
		GSK2857916 0.06 mg/kg (Part 1 MM)	0.06 mg/kg	2
		GSK2857916 0.12 mg/kg (Part 1 MM)	0.12 mg/kg	3
		GSK2857916 0.24 mg/kg (Part 1 MM)	0.24 mg/kg	4
		GSK2857916 0.48 mg/kg (Part 1 MM)	0.48 mg/kg	5
		GSK2857916 0.96 mg/kg (Part 1 MM)	0.96 mg/kg	6
		GSK2857916 1.92 mg/kg (Part 1 MM)	1.92 mg/kg	7
		GSK2857916 2.50 mg/kg (Part 1 MM)	2.50 mg/kg	8
		GSK2857916 3.40 mg/kg (Part 1 MM)	3.40 mg/kg	9
		GSK2857916 4.60 mg/kg (Part 1 MM)	4.60 mg/kg	10
		GSK2857916 3.40 mg/kg (Part 2 MM)	3.40 MM	11
		GSK2857916 3.40 mg/kg (Part 2 NHL)	3.40 NHL	12

Notes:

^[1] This is a single-arm study and only active treatment is planned for the study.

^[2] Part 1: dose escalation phase; Part 2: Expansion Cohort; MM: multiple myeloma; NHL: Lymphoma.

5.2. Baseline Definitions

For all endpoints (except as noted in baseline definitions) the baseline value will be the latest pre-dose assessment with a non-missing value, including those from unscheduled visits. If time is not collected, Day 1 assessments are assumed to be taken prior to first dose and used as baseline.

For subjects who did not receive study treatment during the study, baseline will be defined as the latest, non-missing collected value.

For ECG analyses, subject level baseline is defined as the mean of triplicate baseline assessments.

Unless otherwise stated, if baseline data is missing no derivation will be performed and baseline will be set to missing.

5.2.1. Examination of Subgroups

The list of subgroups may be used in descriptive summaries. Additional subgroups of clinical interest may also be considered.

Subgroup	Categories
Age	18 to <65, 65 to <75, >=75
Sex	Male, Female
Ethnic Background	White, Other
ISS Staging at Screening	I, II, III, Other (Unknown or Missing)
Number of prior lines of therapy	<=3,4-5, >5
Type of myeloma	IgG, Non-IgG
Prior Daratumumab Treatment	Yes, No
Refractory to prior anti-cancer therapy	Any Proteasome Inhibitor (PI) Bortezomib Carfilzomib Ixazomib Any Immunomodulator (IMiD) Thalidomide Lenalidomide Pomalidomide Monoclonal Antibodies Daratumumab Daratumumab alone ^[1] Daratumumab in combination ^[2] PI+IMiD Daratumumab+PI+IMiD Penta-refractory ^[3]
Cytogenetics Risk ^{[4]w}	High, Other (non-high risk, not done, or missing)
Prior anti-cancer therapy of interest	
 • With prior Daratumumab Treatment and Refractory to Both Immunomodulators and Proteasome Inhibitors. • Without prior Daratumumab Treatment. • Refractory to Both Immunomodulators and Proteasome Inhibitors.

NOTES:

^[1] Defined as prior CTX regimen with Daratumumab as the only drug in the regimen.

^[2] Defined as prior CTX regimen with Daratumumab and other drugs in the regimen.

^[3] Penta-refractory= refractory to: Bortezomib and Carfilzomib and Lenalidomide and Pomalidomide and Daratumumab.

^[4] A subject is considered as high risk if the subject has any of the following cytogenetics: t(4;14), del17p, t(14;16).

5.3. Other Considerations for Data Analyses and Data Handling Conventions

Other considerations for data analyses and data handling conventions are outlined in the appendices:

Section	Component
16.3	Appendix 3: Assessment Windows
16.4	Appendix 4: Study Phases and Treatment Emergent Adverse Events
16.5	Appendix 5: Data Display Standards & Handling Conventions
16.6	Appendix 6: Derived and Transformed Data
16.7	Appendix 7: Reporting Standards for Missing Data
16.8	Appendix 8: Values of Potential Clinical Importance

6. STUDY POPULATION ANALYSES

6.1. Overview of Planned Study Population Analyses

The study population analyses will be based on the “All Treated” population, unless otherwise specified.

Study population analyses including analyses of subject’s disposition, protocol deviations, demographic and baseline characteristics, prior and concomitant medications, and exposure and treatment compliance will be based on GSK Core Data Standards. Details of the planned displays are presented in [Appendix 12: List of Data Displays](#).

6.2. Disposition of Subjects

A summary of the number of subjects in each of the analysis populations described in Section 4 will be provided (for final analysis, Evaluable population will not be included). In addition, the number of subjects enrolled by center will be summarized by Study Part and Tumor Type using the “Enrolled” population. A separate summary for exclusions from each study population will be displayed (for final analysis, Evaluable population will not be included). A listing of subjects excluded from analysis populations will also be provided.

A summary of subject status and reason for study withdrawal will be provided. This display will show the number and percentage of subjects who withdrew from the study, including primary reasons for study withdrawal. Reasons for study withdrawal will be presented in the order they are displayed in the eCRF.

A summary of study treatment status will be provided. This display will show the number and percentage of subjects who are ongoing or discontinued study treatment and a summary of the primary reasons for discontinuation of study treatment. Reasons for study treatment discontinuation will be presented in the order they are displayed in the eCRF. A listing of study treatment discontinuation will be generated. The listing will include last dose date, and reasons for study treatment discontinuation.

6.3. Demographic and Baseline Characteristics

The demographic characteristics (e.g., age, race, ethnicity, sex, baseline height, and baseline body weight and baseline BMI) will be summarized and listed. Age, height, weight and BMI will be summarized using the mean, standard deviation, minimum, median, and maximum. The count and percentage will be computed for sex and ethnicity.

Race and racial combinations will be summarized and listed.

Disease history and characteristics (e.g. time since initial diagnosis in years, stage at initial diagnosis, date of initial diagnosis) at initial diagnosis and screening will be listed. Separate summaries of disease characteristics at initial diagnosis and screening will be provided. Disease characteristics for multiple myeloma subjects at screening, including stage, lines of prior therapy regimens, type of multiple myeloma, myeloma light chain and myeloma immunoglobulin will be summarized and listed.

Medical conditions present at screening will be listed and will be summarized by past and current and by cancer-related and non-cancer related categories.

Genetic characteristics for multiple myeloma subjects at screening will be summarized and listed. Cytogenetic risk for multiple myeloma subjects at screening will be summarized. A subject is considered as having high cytogenetic risk if the subject has any of the following cytogenetics: t(4;14), del17p, t(14;16).

Substance use, including smoking history and alcohol use will be summarized and listed.

Prior anti-cancer therapy will be coded using GSK Drug coding dictionary, then summarized by type of therapy and listed. A listing of prior anti-cancer therapy will show the relationship between ATC Level 1, Ingredient, and verbatim text. A summary of the best response to the most recent prior anti-cancer therapy will be provided. A summary of the number of prior anti-cancer therapy regimens will also be produced.

Prior anti-cancer therapy for multiple myeloma subjects will also be summarized by type of therapy, drug class and subclass. A summary of multiple myeloma subjects refractory to prior anti-cancer therapy by drug class will be provided.

A multiple myeloma subject is defined to be refractory to prior anti-cancer therapy if

- [1] the subject's best response to prior anti-cancer therapy is PD or SD, **OR**
- [2] the subject's most recent response to prior anti-cancer therapy is PD or SD, **OR**
- [3] the subject progress within 60 days of completion of prior anti-cancer therapy.

Summary of subjects with multiple myeloma double refractory to prior Immunomodulator (IMiD) and Proteasome Inhibitor (PI) will also be provided. For definition of "double refractory", IMiD and PI are not necessary to be in the same regimen.

Anti-cancer radiotherapy will be listed. Prior cancer and non-cancer related surgeries will be summarized. Prior and on treatment cancer and non-cancer related surgeries will be listed.

